**UCSD Human Research Protections Program**  
**New Biomedical Application**  
**RESEARCH PLAN INSTRUCTIONS**

These are instructions are for completing the Research Plan that is available in MS Word format from the [HRPP website](#).

The headings on this set of instructions correspond to the headings of the Research Plan.

General Instructions: Enter a response in for all topic headings.

Enter "Not Applicable" rather than leaving an item blank if the item does not apply to this project.

Version date: 11/15/2016

## **1. PROJECT TITLE**

CHARM2 – Enhancing Male Participation in Interventions to Prevent Unintended Pregnancy

## **3. FACILITIES**

- UCSD, Department of Medicine, Division of Infectious Disease and Global Public Health: Project coordination from US side; **no access to identifiable data**
- National Institute for Research on Reproductive Health, Mumbai, India – **under jurisdiction of a separate IRB in India**
- Homes of study participants for survey assessments, intervention sessions take place in primary health center clinics, located in Maharashtra, India

## **4. ESTIMATED DURATION OF THE STUDY**

The entire study duration is 5 years.

## **5. LAY LANGUAGE SUMMARY OR SYNOPSIS (no more than one paragraph)**

Globally, 41% of all pregnancies are unintended, increasing risk for maternal and infant morbidities and mortality. Most unintended pregnancies occur in the context of contraceptive non-use or failure. Women with husbands not supportive of contraception are more likely to report contraceptive non-use, and women with sexually abusive husbands are more likely to report contraceptive failure. Such findings highlight the need for family planning (FP) interventions that engage both women and men, focus on eliminating marital sexual violence (MSV) and promote use of effective (low failure risk) spacing contraception including long-acting reversible contraception (LARC; e.g. intrauterine device or IUD). Rural India, with some of the lowest rates of contraception and highest rates of marital violence globally, offers an important context in which to test such interventions, with global implications. Prior research from this team documents promise of the original CHARM intervention, a gender equity (GE) FP intervention engaging men and delivered by male health providers over three months. This intervention improved contraceptive use and reduced likelihood of MSV, but demonstrated no reduction in unintended pregnancy; additionally, it demonstrated good participation from men (91%) but less from couples (51%), largely due to women's discomfort with a male provider. Poor reach to women and provision of only short-acting contraceptives (pill, condom) more vulnerable to contraceptive failure, likely compromised unintended pregnancy outcomes. Based on these findings, we propose CHARM2, which will include CHARM sessions for men AND parallel women-focused GE+FP sessions delivered by a female provider and inclusive of broader contraceptive options, including LARC, as well as a combined couples session. This study seeks a) to implement CHARM2, b) to evaluate its impact on contraceptive use, unintended pregnancy, and MSV with rural couples in India, and c) to assess its potential for sustainability in rural India, using implementation science methods. To evaluate the impact of CHARM2 on our outcomes of interest, a two armed cluster randomized controlled trial will be conducted with N=1200 married couples from 20 geographic clusters (n=60 couples per cluster) in rural Maharashtra, India. Participants will receive CHARM2 or the standard of care (SOC) control condition, which will involve community health workers offering pills/condoms and linking women to public health clinics. Outcomes for both intervention and SOC participants will be assessed via pregnancy testing and surveys at baseline and 9 & 18-month follow-ups. Implementation science methods will be used to assess the quality, scalability, and replicability of CHARM2 for uptake by rural health care systems (i.e., sustainability). Specifically, in-depth interviews (IDI) will be conducted with CHARM2 intervention couples (n=50), providers (n=20); 5-7 focus group discussions (FGDs) will be conducted with mother in laws (MILs) of couples that participate in IDIs, and key stakeholders from the family planning and rural health infrastructures at state, national and international levels (n=50), and we will implement a cost-effectiveness analysis of CHARM2.

## **6. SPECIFIC AIMS**

1) To implement the CHARM 2 GE+FP intervention, comprised of CHARM sessions with men and parallel sessions with women, and inclusive of broader contraceptive options including LARC, as well as one combined couples session. Men's sessions will be delivered by male health providers; women's sessions will be delivered by public Auxiliary Nurse and Midwives (ANMs), or a trained provider/counselor. The couple's session will be delivered by an ANM, trained provider, or counselor.

2) To evaluate the impact of CHARM2 on spacing contraceptive use (including LARC), unintended pregnancy, and MSV via a two armed cluster RCT with N=1200 married couples from 20 geographic clusters (n=60 couples per cluster) in rural India. The control arm will receive SOC in the form of community health workers offering pills/condoms and linking women to public health clinics. Outcomes will be assessed via pregnancy testing and surveys at baseline, 9 and 18-month follow-ups.

**Hypotheses:** We hypothesize that CHARM2 participants will be more likely than SOC participants to:

- a) Use contraception (including LARC) at 9 & 18-month follow-ups; effects on LARC will be explored
- b) Be less likely to report marital sexual violence (MSV) at 9 & 18-month follow-ups
- c) Not have an unintended pregnancy over the 18-month follow-up period.

3) To assess the quality, scalability, and replicability of CHARM2 for uptake by rural health systems (i.e., sustainability), using implementation science methods including IDI with CHARM2 couples (n=50) and providers (n=20), 5-7 focus groups with MILs of couples that participate in IDIs, control condition couples (n=20), and key stakeholders from the FP and rural health infrastructures at state, national and international levels (n=50), survey of healthcare facilities in the study area (n approximately=250), and a cost-effectiveness analysis.

Should CHARM2 prove effective and sustainable, study findings will have broad implications for FP interventions for low resource settings in India and elsewhere.

## 7. BACKGROUND AND SIGNIFICANCE

India still faces high unintended pregnancy (3.3 million pregnancies, annually) and unmet need for spacing (use of LARCs is <10% in rural India). Moreover, there is a gender-based barrier to accessing contraception, especially among the youngest (15-24 years) wives. Though male engagement in FP is recommended, there is little evaluated work in this area. The CHARM study effectively demonstrated impact of a GE+FP intervention on contraceptive use through counseling on gender equitable decision-making. CHARM2 is a brief GE+FP intervention that builds on the proven CHARM approach to engage husbands. CHARM2 aligns with recent policy efforts made by the Indian government to increase LARC use. These policies offer free provision of IUDs (Copper-T), and more recently, injectables. CHARM2 also supports recommended training of public health ANMs on IUD provision. CHARM2 is significant as it uses a proven theoretical model that utilizes male engagement, to improve use of LARCs to address the unmet need for spacing in rural India.

## 8. PROGRESS REPORT

This application is a resubmission.

## 9. RESEARCH DESIGN AND METHODS

**Overview:** This study will involve 3 phases: Phase 1- the Preparatory Phase to map the project area and prepare communities for the planned research. Phase 2- Implementation and Evaluation of CHARM 2 (Aims 1&2), using a two-armed cluster randomized controlled trial (RCT) in 20 geographic clusters mapped in Phase 1. To assess treatment impact on contraceptive use, MSV and unintended pregnancy, clusters will be randomized to receive CHARM2 or the control program, which includes SOC public health FP services. Intervention effects will be assessed via surveys and pregnancy testing at baseline and 9 &18-month follow-up with n=1200 couples (wife 18-29 years). Phase 3- Implementation Science Assessments will include IDI with CHARM2 providers (n=20), select CHARM2 couples (n=50), MILs for those IDI couple participants that are comfortable with MIL participation, control condition couples (n=20), and key Indian stakeholders in FP & public health (n=50). Interviews with providers and couples will explore intervention delivery and perceived impact. Interviews with FP & public health stakeholders will obtain feedback on perceived feasibility to sustain and scale up CHARM2. A survey of all healthcare facilities in the study area (n approximately=250) will support understanding of the local healthcare context as well as access to and availability of family planning in the study communities. A cost-effectiveness analysis will also be done to support considerations of sustainability.

**Procedures/Activities for Participants:** Phase 1 of the study is preparatory stage for cluster randomization and training of providers. In phase 2 and phase 3, the participants will participate in the trial at the villages where they reside. NIRRH staff will conduct survey assessments with participants in the homes of the participants, after obtaining permission to do so. Intervention sessions with male providers and ANMs or trained providers/counselors will take place in at home, or in clinic settings. In Phase 2, the participants will complete survey assessments at baseline, and 9 &18-month follow-up. Female participants (wives) will also take urine pregnancy tests at baseline, and 9 &18-month follow-up. In phase 3 a subsample of CHARM2 couples (n=50) will participate in IDIs at 9 month follow-up to describe their experiences with the intervention and their views of its utility, as well as their perceptions related to its outcome effects. All CHARM2 providers (n=20) will be asked to participate in IDIs at their facility to assess their perceptions of CHARM2 quality, acceptability and utility. A subsample of control condition couples (n=20) will participate in IDIs at 18 month follow-up to describe their experiences with family planning and gender-based violence in the study area context but outside of the intervention. Healthcare facilities in the area will be mapped and information will be collected on whether the facility provides family planning, what methods they provide, and whether the facility participated in the CHARM2 intervention.

**The CHARM2 Intervention:** CHARM2 intervention will involve gender, culture and contextually-tailored FP+GE counseling sessions delivered individually to husbands by a trained male health provider (2 sessions), and, in parallel, delivered individually to wives by a trained female ANM or trained provider/counselor (2 sessions), as well as a combined couples session. CHARM2 differs from the original CHARM intervention by adding parallel sessions for wives, delivered by the ANM, and including LARC counseling for husbands and wives and opportunity for LARC provision in the sessions with women. The ANM or trained provider/counselor session will use GE counseling from the CHARM couple session with public health FP and LARC counseling. Sessions will be provided at the participants' home or within the clinical setting, as the husband and wife prefer. The 5 sessions will be delivered across 3 months with a minimum of 1 week between the men's sessions; the men's Session 1 must be delivered before the female session.

**SOC Control Condition:** Under India's public health system, ASHAs and ANMs provide household visits to women to increase awareness and use of FP services, with ASHAs incentivized to bring women to PHCs for FP services and ANMs rarely providing contraceptives. For those women or couples that reach the PHC, SOC FP counseling and services are delivered by a physician; free contraceptives are then offered, most often female sterilization and rarely LARC. Control group female participants will be linked with ASHAs to support access to PHC FP services. ANMs will not provide LARC or GE counseling for control condition women. Men will receive no FP counseling.

**Timeline:** Phase 1 of the study preparation will take approximately 3 months. Phase 2 will be in month 4 to month 60, including enrollment and intervention start at month 4, 9 month follow up at month 13, and 18 month follow up at month 22. The outcome analysis will also be carried out in this phase at month 40. Phase 3, on sustaining the intervention, will overlap from month 7 to month 60.

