## **Quantitative Data Collection:**

Survey and urine pregnancy test data (from wives) will be collected from all enrolled couples in the CHARM2 RCT evaluation study. Both intervention and SOC arm participants will provide survey data at baseline and 9 & 18 month follow-ups. Survey data will be collected electronically on tablets using a unique identifier to link data between couples and across time. Wives in both the intervention and the SOC arms will be tested for pregnancy using a urine specimen at baseline and at both post-test timepoints; these data will directly be entered into the password protected electronic survey system at the time of survey data collection. Urine samples for pregnancy testing will not be retained for the study, but will be disposed of in disposal facilities upon completion of the test. Survey and pregnancy test results data will be stored locally on the tablet and, when internet is available, uploaded to the password-protected server. Separately, a list of contact names with unique identifiers will be maintained for tracking purposes; a hard copy form of this list will be kept in a locked file in [name] locked office at NIRRH. Baseline and follow-up surveys will be collected from couples using measures from the original CHARM study, which was based on India's Demographic and Health Survey (DHS/India's NFHS-3) and other validated measures. Couples must meet the eligibility criteria outlined below.

Eligible couples will be:

- Young wives (aged 18-29 years) and their husbands
- couples fluent in Marathi and both willing to participate
- no sterilization or infertility indicated (infertility is defined as having no pregnancy for 1+ years despite non-use of traditional or modern contraception)
- no pregnancy or female/male surgical sterilization planned for the next 18 months, and no reported use of consistent use of modern contraceptives in the past three months, and
- residing in the village for at least 2 years and residing together for at least 3 months, to facilitate follow-up tracking

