The primary analyses will use an intent-to-treat approach and analyze all subjects according to randomized group. For subjects missing month 9 or 18 endpoints, these will be multiply imputed from the lower (worse) half of the distribution from their arm (conservative approach). Additional analyses will be conducted using a per protocol approach that includes only those subjects who complete the full intervention. Analyses will use women's data only; however, men's data will be used to validate outcomes a) increased contraceptive use, and b) reduced unintended pregnancy. Exploratory analyses using outcomes of contraception by type (e.g., LARC) may be conducted if numbers are sufficient across time-points.

At 18 month follow-up, healthcare facilities in the study area will be surveyed to assess provision of FP counseling and methods, availability of FP methods, approximate FP method client volume, provider type/qualifications, and participation in the CHARM2 intervention. Healthcare facility location GPS will be collected for mapping of healthcare services in the study area; no personally identifying information regarding the providers will be collected.

At 18 month follow-up, participants' location data will be re-collected in the form of GPS coordinates; this data will be used to examine distances to healthcare facilities in the study area. GPS data will be collected in a separate survey form to be accessed only by NIRRH in-country study staff. In-country study staff may use this location data, in conjunction with healthcare facility location data, to calculate participant-level distance to healthcare providers. Geolocation data will **not** be shared with UCSD or any other external sources; any maps produced which visualize healthcare facility location and access will **not** include participant locations. Calculated distances **only** may be shared with UCSD analysts, to be summarized and utilized in adjusted regression models to better understand drivers of and barriers to health care services generally, and family planning services specifically, in the study area.

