## 11. RECRUITMENT

This study involves randomization at the geographic cluster rather than individual level. While individual randomization is more powerful, cluster randomization allows us to reduce risk for contamination that may occur if both treatment conditions were offered in the same geographic area. Participating couples will be recruited from geographic clusters of approximately equal size mapped for randomization. Clusters are geographically distinct areas with administrative boundaries, natural borders and appropriate distance from other study clusters to reduce risk for contamination. Clusters will be created based on geographic boundaries, population density (approximately 5000 population per cluster), and proximity to ANMs and health providers. Clusters will be selected based on minimum number of eligible couples (at least 60 eligible couples); clusters will then subsequently be randomized to intervention or control conditions using computer-generated random numbers. Households within each cluster will be screened sequentially for eligibility. Research staff are not to be blinded to the treatment condition assignment to clusters. Recruitment of eligible households will be n = 60 per cluster. In a small cluster if the total number of eligible couples is equal to 60, all couples are approached for recruitment. In a larger cluster if the eligible couple number is more than 60, the required number of couples will be selected through systematic random sampling (selecting every nth participant).

Trained NIRRH survey research teams (1 male & 1 female) will approach selected households for screening and recruitment. Three attempts to reach the couple will be made for each selected household. If an eligible household has two or more couples meeting eligibility criteria, a Kish Grid will be used to determine the participants. Couples selected from eligible households will be asked to join the study and will be informed that the study focuses on FP. Data will be collected to assess participation rates and biases by

age, and contraceptive use. Recruitment/enrollment and intervention delivery will occur over 2.5 years on a rolling basis.

**PLEASE NOTE:** No identifiable information will be collected from those screened and found to be ineligible or unwilling to participate, across study phases.

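### The outcome analysis is dated at month 40, but 2.5 years of rolling enrolment puts the last 18-month visits at about months 49 to 52

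*Combined protocol and SAP*

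**What the plan says.** The Timeline paragraph of section 9 gives "enrollment and intervention start at month 4, 9 month follow up at month 13, and 18 month follow up at month 22". On the outcome analysis it says: "The outcome analysis will also be carried out in this phase at month 40". The phase meant is Phase 2, which runs from month 4 to month 60.

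Section 11 (Recruitment) says: "Recruitment/enrollment and intervention delivery will occur over 2.5 years on a rolling basis". For each couple, section 9 says: "The 5 sessions will be delivered across 3 months with a minimum of 1 week between the men's sessions". Every couple is then followed for 18 months: "Both intervention and SOC arm participants will provide survey data at baseline and 9 & 18 month follow-ups".

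Two other places bear on the point. The sample size text in section 9 bases all three power figures on the 18-month time point alone. For subjects without a month 9 or month 18 endpoint, the Quantitative Data Collection text says "these will be multiply imputed from the lower (worse) half of the distribution from their arm".

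**The concern.** Months 13 and 22 are the dates for a couple enrolled in month 4. Under rolling enrolment they are the first follow-up visits, not the dates of follow-up as a whole. No section gives the month of the last visit, ties the outcome analysis to completion of 18-month follow-up, or describes the month-40 analysis as partial.

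Followed as written, the outcome analysis would be run while some couples are still in follow-up. The 18-month comparison is the one on which the study was sized, and unintended pregnancy is defined over the whole 18 months. The imputation rule adds a risk: it does not separate a visit that was missed from one that is not yet due, so it could be misapplied to couples still in follow-up.

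**Working it through.** **Inputs.** Enrolment starts at month 4, the outcome analysis is at month 40, and sessions take 3 months per couple (section 9). Enrolment and delivery take 2.5 years = 30 months (section 11). Observed couples number 960, so 480 per arm; for unintended pregnancy the plan compares 90% with 95.5% at kappa = 0 and states 89.5% power (section 9, sample size). The study lasts 60 months (section 4).

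**The plan's own dates.** 4 + 9 = 13 and 4 + 18 = 22. Both reproduce, for month-4 enrolment only.

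**Last 18-month visit.** The window closes at month 4 + 30 = 34.
- If the 30 months include the last couple's sessions, last enrolment is 34 − 3 = 31 and the last visit is 31 + 18 = 49.
- If enrolment itself runs to month 34, the last visit is 34 + 18 = 52.

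These are 9 and 12 months after month 40. If the 2.5 years are counted from month 1, last enrolment is month 28 or 31 and the last visit month 46 or 49.

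**Share without an 18-month visit at month 40.** Only couples enrolled by month 40 − 18 = 22 can have it. Let E be the last enrolment month. The documents do not describe accrual, so each row is an assumption.

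| Accrual from month 4 | Formula | E = 31 | E = 34 |
|---|---|---|---|
| Even | (E − 22)/(E − 4) | 9/27 = 33.3% | 12/30 = 40.0% |
| Falling linearly to zero | [(E − 22)/(E − 4)]² | 11.1% | 16.0% |
| Rising linearly from zero | 1 − [18/(E − 4)]² | 55.6% | 64.0% |

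Of 1200 couples, even accrual leaves 400 to 480 without the visit. Counted from month 1, even accrual gives 6/27 = 22% to 9/30 = 30%.

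**9-month visits.** These are due by month 40 for couples enrolled by month 31: all of them if E = 31, and 27/30 = 90% under even accrual if E = 34.

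**Power for unintended pregnancy** (two-sided 5% level assumed; no clustering, since kappa = 0). Even accrual leaves 480 × 0.60 = 288 to 480 × 2/3 = 320 observed couples per arm. Two normal approximations were used:
- Risk difference: Φ[(0.055 − 1.96·SE₀)/SE₁], where SE₀ = √(2 × 0.9275 × 0.0725/n) and SE₁ = √((0.90 × 0.10 + 0.955 × 0.045)/n).
- Log-odds: Φ[ln OR/SE − 1.96], where ln OR = ln(0.955/0.045) − ln(0.90/0.10) = 0.858 and SE = √(34.38/n). The 34.38 is 1/(0.90 × 0.10) + 1/(0.955 × 0.045).

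| Couples per arm | Risk difference | Log-odds |
|---|---|---|
| 480 (plan states 89.5%) | 90.9% | 89.3% |
| 320 | 76.6% | 74.4% |
| 288 | 72.2% | 69.9% |

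Both methods come within 2 points of the stated power at full size.

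**The case against.** The strongest defence is that month 40 is a planning milestone that was never updated, not a decision to analyse incomplete data. Section 15 supports this. Its interim efficacy analysis is triggered when half of subjects have completed the 18-month visit, which suggests a final look on full completion. That makes a deliberate partial analysis unlikely, but the document nowhere says so, and the calendar date is the only rule given for the outcome analysis. Nor is month 40 the interim look: that is a separate analysis triggered by subject count, and under even accrual from month 4 it would fall at about months 35.5 to 37.

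Several stronger readings are tempting and not supported:
- **That a third or more of the 18-month data would certainly be absent.** This needs even accrual from month 4, which is not stated.
- **That the plan would impute unfavourable outcomes for couples not yet due.** The rule addresses missing endpoints, and a visit not yet due is not normally counted as missing. The wording leaves room for misapplication; it does not direct it.
- **That specific power losses follow for contraception and marital sexual violence.** These depend on how kappa is converted and on the number of villages per cluster, which the document does not give, so no figure is offered.
- **That every endpoint is affected alike.** The 9-month comparisons for contraception and marital sexual violence would be nearly or fully available.

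The power figures above are also for observed couples at 18 months only. The planned longitudinal model uses further time points, and the plan says its power will be higher.

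**Conclusion.** The inconsistency stands. A 2.5-year enrolment and delivery period, whether counted from month 4 or month 1, puts the last 18-month visits after month 40: at about months 49 to 52, or 46 to 49. That conclusion needs only the plan's own dates.

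The size of the gap is less certain. It is 33–40% of couples if accrual is even from month 4, and about 11–64% over the other shapes considered. For unintended pregnancy the even-accrual case means power of about 70–77% instead of 89.5%. The problem is confined to the 18-month endpoint. It is an error of scheduling that wording can correct, not evidence that the sponsor intends to analyse incomplete follow-up.

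**What to change.** In the section 9 Timeline, replace the month-40 date with a completion rule: *the outcome analysis follows the last enrolled couple's 18-month visit and database lock*. Under the stated enrolment this is about month 52 or later (month 49 at the earliest if the 30 months include the last couple's sessions). Relabel months 13 and 22 as the first 9- and 18-month visits. It would also help to say that the imputation rule applies only to visits already due.

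If month 40 is to stand, amend section 11 instead so that enrolment closes by month 22, which is 18 months of accrual rather than 30.

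The first option costs only wording and a final result up to about a year later. Last visits at months 49 to 52 leave 8 to 11 months before month 60. The second option would require the same 1200 couples to be enrolled in 18 months.
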